#### **5.5.5 Assessment of Toxicities**

Treatment-emergent adverse events will be enumerated and analyzed according to the incidence, intensity, type of adverse events, and clinically significant changes in the patient's physical examination findings, vital signs and clinical laboratory results. Safety variables will be tabulated and presented for all patients in the safety and per-protocol populations as defined previously.

Adverse events will be graded and coded using the NCI Common Terminology Criteria for Adverse Events (CTCAE, Version 4.03). Treatment-emergent events will be tabulated, where treatment-emergent is defined as any adverse event that occurs after administration of the first dose of study drug and through 30 days after the last dose of study drug, or any event that is present at baseline and continues after the first dose of study treatment but worsens in intensity. Events that are considered related to treatment (possibly, probably or definitely drug-related) will also be tabulated separately. Tables that enumerate adverse events by severity will be provided. Deaths, serious adverse events and events resulting in study discontinuation will be tabulated in data listings including additional relevant information on each patient. Tables will be presented both overall (all arms combined), by each treatment group separately, and by cell. Where appropriate, statistical comparisons between treatment arms will be provided using the above-mentioned methods for analysis of categorical data.

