#### **8.2.6. Initial 24 Month Treatment Intervention Early Termination (+ 2 weeks)**

Within 2 weeks off final study pill treatment for any cause, all subjects will have a follow-up history and physical exam/review of body systems (including, weight and vital signs), along with toxicity assessment. Repeat blood laboratory tests (CBC, chemistry panel, and urinalysis), a random urine sample will be obtained for polyamine determination, EKG (Subject needs to be in the supine position for 10 minutes prior to the EKG) and audiometry will be performed. Women

of child bearing potential will also have a serum pregnancy test performed. Concomitant medications, adverse events and medication compliance will also be reviewed. Quality of life questionnaires (EORTC QLQ-C30, EORTC QLQ-CR29, EQ-5D and the modified Cancer Worry Scale) will be provided to the subject to complete. A food frequency questionnaire will be provided to the subject to complete at North American (United States and Canada) sites only.

Repeat upper and lower endoscopies with image and video documentation will be obtained at the Month 24/EOT visit or if the subject has completed at least 3 months of treatment from the previous on-study upper and lower endoscopy procedures (including baseline). A normal mucosal biopsy sample for polyamine determination will be obtained during the colonoscopy/proctoscopy procedure.

If the subject has an unscheduled upper/lower endoscopy for any reason, these procedures should be captured with image and video documentation including the collection of a normal mucosal biopsy, if possible. A random urine sample should be obtained for polyamine determination, if possible.

Subjects will be formally taken off-study treatment and complete the End of Treatment (EOT) assessments if there is a cumulative delay/suspension of study medication for any reason of:

- > 90 days from randomization to month 36
- > 105 days from randomization to month 42
- > 120 days from randomization to month 48

A temporary suspension from taking study medication as stated above (for example, due to a non-FAP disease related surgery or procedure), will be documented as a treatment delay and the subject will continue on study, on their original schedule.

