#### **8.2.7. Initial 24 Month Treatment Intervention Follow-Up (30-days post end of treatment visit +/- 1 week) Off Study**

Thirty-days (30) after completion of the end of study evaluations, subjects will be contacted by phone for a clinical update in regard to symptoms and interval medical history. Concomitant medications and adverse events will also be reviewed. The subject will provide a clinical update and procedure date for any FAP-related surgical event or major endoscopic excisional event that has occurred since the last contact. These include partial colectomy, colectomy with IRA, total procto-colectomy, proctectomy, pouch resection, sub-mucosal resection, trans-duodenal excision, ampullectomy, duodenectomy, or Whipple procedure.

An FAP-related event at any disease site (colon/rectum/pouch, duodenum) will lead to discontinuation of the study treatment but follow-up of the subject will continue until the end of the 30 day follow-up period.

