### **11.2. Ototoxicity Risk**

All subjects will undergo air conduction audiology for hearing impairment as part of the screening process and at months 12, 24, 36 and 48/end of treatment. Subject diaries will indicate the presence of symptoms and will instruct the subject to contact the treating doctor for assessment. These data will not be used to exclude subjects from this study.

At months 3, 6, 12, 18, 24, 30, 36, 42 and 48/end of treatment, the subject will undergo a clinical assessment for ototoxicity adverse events symptoms by the research nurse or other medically qualified individual.

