## **11.7. Reporting of AEs, SAEs, Serious and Unexpected Adverse Experiences**

### **Subject Reporting of an Adverse Event**

Subjects will be instructed to contact the Investigator or Research Nurse to report any symptom. The Investigator will question each subject regarding symptoms at the time of each physical examination/review of body systems. All adverse experiences, including duration and severity will be captured in the Case Report Forms provided by the Sponsor.

All adverse events are to be documented from the day the subject receives his/her first study treatment through 30 days after the subject’s off study treatment date (date of last dose).

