### **5.5.2 Patient Disposition and Treatment Summaries**

Subjects will be assigned for analysis to the treatment group to which they were randomized, regardless of whether the patients received any treatment.

Patient disposition and treatment will be summarized for the ITT and safety populations defined previously (see Section 4.2). Patient disposition will be consistent with the CONSORT criteria[6], and will include per treatment group enumeration of all patients randomized, the number deemed ineligible, the number of FAP-related events, and the number of study drop outs. These will be further described in subgroups such as drop outs due to adverse events, serious adverse events, administrative withdrawals for non-compliance for more than 90 days from randomization to month 36 or more than 105 days from randomization to month 42 or more than 120 days from randomization to month 48, withdrawals of consent for continued follow-up, withdrawals for other reasons, and the number lost to follow-up. Additional summaries will include reasons for patients discontinuing treatment and/or modifying treatment dosages. A listing of screened and ineligible patients along with the reason for each also will be summarized.

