#### **5.5.4 Analytic Methods for Categorical or Continuous-Valued Secondary Outcome and Safety Data**

For categorical data, comparisons will be made between treatment groups using standard chi-squared techniques as the primary approach. In particular, the Cochran-Mantel-Haenszel one degree of freedom test will be used to reflect the stratified randomization. Exact p-values and 95% confidence intervals by the point-probability method will be reported[1].

For continuous endpoints, standard analysis of covariance (ANCOVA) methods will be used as the primary approach to compare treatment groups at end of treatment with the following covariates: baseline value, binary indicator variables for the two highest-risk stratification levels used in the randomization (using the lowest-risk, i.e., rectum/pouch polyposis, group as the reference stratum), and a binary treatment indicator (1=combination treatment, 0=single treatment).

For ordered categorical data, a Kruskal-Wallis nonparametric test for ordered categorical response will be used to compare treatment groups[5].

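### If the combination delays FAP events, its patients are observed for adverse events longer, and the planned between-arm comparison of adverse events makes no allowance for time at risk

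*SAP*

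**What the plan says.** **Analysis.** SAP 5.5.5: "Treatment-emergent adverse events will be enumerated and analyzed according to the incidence, intensity, type of adverse events". On tests between arms it adds: "Where appropriate, statistical comparisons between treatment arms will be provided using the above-mentioned methods for analysis of categorical data". Those methods are in SAP 5.5.4: chi-squared techniques, in particular a one-degree-of-freedom Cochran-Mantel-Haenszel (CMH) test over the randomization strata, with "Exact p-values and 95% confidence intervals by the point-probability method will be reported". Protocol 12.6.3 carries the same plan. Neither text gives a patient-time rate, a time-to-first-AE analysis or a fixed-window comparison.

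**Observation window.** Protocol 8.2.7: "An FAP-related event at any disease site (colon/rectum/pouch, duodenum) will lead to discontinuation of the study treatment"; Protocol 8.3.2 lists the same event as a reason for withdrawal from treatment. Protocol 11.7: "All adverse events are to be documented from the day the subject receives his/her first study treatment through 30 days after" the off-treatment date, which it equates with the last dose. SAP 5.5.5 uses the same 30-day limit for treatment-emergent events. Event-free patients may stay on drug for up to 36, 42 or 48 months (Protocol 4.2).

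**Exposure.** SAP 5.5.2: "Patient disposition and treatment will be summarized for the ITT and safety populations defined previously". It goes on to reasons for stopping and dose modification, and does not name duration of treatment. The table shells are held outside the SAP (7.2).

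**Hearing tests.** Audiometry is done "as part of the screening process and at months 12, 24, 36 and 48/end of treatment" and at early termination (Protocol 8.2.6), so patients who stay on longer are also tested more often.

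**The concern.** The trial hopes to show that the combination delays FAP events. If it does, combination patients stay on drug, and under AE collection, for longer. Efficacy is analysed as time to event, which handles unequal follow-up. AEs would be compared as simple proportions, as if follow-up were equal. An AE that accrues with time can then appear more often on the combination when its hazard is the same in both arms, and a reader of the safety tables could take the difference for added toxicity. The distortion grows with the efficacy effect, so it is largest when the AE tables matter most for weighing benefit against risk.

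**Working it through.** **1. The plan's own figures.** SAP Table 3.2 assumes 30% and 60% event-free at 24 months with exponential times. The hazards are -ln(0.3)/24 = 0.0502 and -ln(0.6)/24 = 0.0213 per month. The medians ln 2/hazard are 13.817 and 32.566 months, and the hazard ratio is ln(0.6)/ln(0.3) = 0.4243. All reproduce.

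**2. Matching to observed events.** Protocol 3.2 reports 171 randomized (57 per arm if equal) and 53 events as of June 2017, fewer than designed. Assumptions: uniform accrual July 2014 to April 2016 (22 months); exponential times; every event-free patient continues to the cap; no other dropout. Protocol 4.2 then gives a cap of 48 months to 10/22 of patients, 42 to 6/22 and 36 to 6/22. For a given hazard ratio (HR), the single-agent hazard h is solved from 57 x [2F(h) + F(HR x h)] = 53 at 35.5 months after 1 July 2014, where F is the mean event probability by that date. At HR 0.4243 this gives 0.01943 and 0.00824 per month, that is 63% and 82% event-free at 24 months.

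**3. Time on drug.** With cap T, the mean is (1 - exp(-hT))/h. At HR 0.4243:

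- Single agent: 31.2, 28.7 and 25.9 months for caps 48, 42 and 36; weighted mean 29.1.
- Combination: 39.6, 35.5 and 31.2 months; weighted mean 36.2.
- Ratio 36.2/29.1 = 1.24.

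**4. Crude AE incidence, equal AE hazard a in both arms.** For cap T and a 30-day tail, the proportion with an AE is 1 - exp(-a x tail) x [h/(h+a) x (1 - exp(-(h+a)T)) + exp(-(h+a)T)], averaged over caps. The values a = 0.01 and 0.02 per month are assumed. A false excess means two-sided p of 0.05 or less with the combination higher, 57 per arm, unstratified; the nominal rate is 2.5%. Pairs in the last two columns are for a = 0.01 / 0.02.

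| HR | Months on drug, single vs combination | Incidence, a = 0.01 | Incidence, a = 0.02 | False excess, Fisher | False excess, chi-square |
|---|---|---|---|---|---|
| 0.4243 | 29 vs 36 (1.24) | 25% vs 30% | 42% vs 51% | 6.5% / 9.9% | 9.5% / 13.7% |
| 0.6 | 30 vs 34 (1.15) | 26% vs 29% | 43% vs 49% | 4.0% / 5.3% | 6.1% / 7.8% |
| 0.8 | 31 vs 33 (1.07) | 26% vs 28% | 44% vs 47% | 2.4% / 2.8% | 3.9% / 4.2% |
| 1 | equal | equal | equal | 1.6% / 1.5% | 2.6% / 2.4% |

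**5. Stratified tests, as the SAP writes them.** A simulation used three strata of 19 per arm, with FAP hazards in the ratio 1:1:3.32 (50%, 50% and 10% two-year event-free, from SAP Table 3.1). At HR 0.4243 the false excess is 8.5% / 13.2% for CMH and 5.7% / 9.6% for the exact test. A stratified log-rank test on time to first AE stays at 2.1-3.1% throughout. For an early-onset AE (20% risk within 3 months) CMH gives 2.2-2.7% and the exact test 1.4%, so there is no inflation.

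**6. Rates the Protocol itself gives.**

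- Cardiovascular (2.7.1): 9 of 184 on placebo and 16 of 191 on the combination, over three years of treatment (2.3). As a constant hazard, -ln(1 - 9/184)/36 = 0.0014 and -ln(1 - 16/191)/36 = 0.0024 per month. At HR 0.4243, incidence is 4.1% vs 5.1% and 6.9% vs 8.5%, a gap of 1.0-1.6 points. The false excess is 0.8-1.9% (Fisher) or 3.8-4.8% (chi-square).
- Hearing: the rate depends on the definition and the trial. Section 2.7.2 (2.9% and 9.3% over three years) implies 0.0008 and 0.0027 per month. Section 5.1.1 (33.6% and 45.2% over 3-5 years) implies about 0.007 to 0.017, which overlaps the assumed range.

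**The case against.** **The count is not wrong.** If an effective combination keeps patients on drug longer, the extra AEs are real and belong in the safety tables. This stands. A reader might infer that the plan overstates the toxicity of the combination; the documents do not support that. The problem is confined to reading the between-arm comparison as AE risk for equal time on drug.

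**Cardiovascular events are too rare for the larger error rates.** This stands too. A reader might carry the 9.5-14% over to cardiovascular events because they are a named risk; at the Protocol's own rates the effect is small (step 6). This trial also excludes patients with the listed cardiovascular risk factors (Protocol 6.2), so its rates could be lower still.

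**The tests are optional.** They are run only where appropriate, with no decision rule attached. That limits the consequence. It does not change which method is written for the cases where a test is run.

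**Exposure may be tabulated already.** SAP 5.5.2 promises treatment summaries and the shells are not in the documents, so an exposure table cannot be ruled out. It would let readers see the imbalance, but the written comparison would still be categorical. The promise in SAP 5.5.6 to continue follow-up after discontinuation does not extend the AE window.

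**The model has no stopping for toxicity that differs by arm.** Correct: more such stops on the combination would narrow or reverse the gap. That too is a reason to analyse by time at risk.

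**Conclusion.** The point holds as a gap in the comparison method. If the combination works, the categorical comparison mixes AE risk with time on drug and can show an excess of common, time-accruing AEs on it when the hazards are equal. At the design hazard ratio the exposure ratio is about 1.24, with the false-excess rates in the first row of the table; the effect is modest at 0.6 and small at 0.8. The pooled 53 events do not identify the true hazard ratio, and the common-AE hazards are assumed.

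A reader might also apply the original design rates, which give 17.6 against 28.1 months on drug (ratio 1.60). That is an upper bound that the observed event rate did not reach.

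Early-onset AEs are barely affected, the primary efficacy result is untouched, and the bias does not hide harm from the combination. The change should be made because it is cheap and the written method is the weaker one; the validity of the trial does not depend on it.

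**What to change.** In SAP 5.5.5 and Protocol 12.6.3:

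1. Keep crude incidence as description.
2. Summarise time on drug by arm, if the separate table shells do not already do so.
3. Where arms are compared on AEs, use time from first dose to first AE (Kaplan-Meier, with a stratified log-rank test or Cox model on the primary strata), censored at last dose plus 30 days. For audiogram shifts, seen only at scheduled tests, use an interval-censored version.
4. Give exposure-adjusted rates only as a supplement, because they assume a constant hazard.
5. State the assumption behind item 3: within stratum, AE risk is unrelated to the timing of the FAP event.

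The cost is wording, a few extra tables and that stated assumption. AE and dosing dates are already collected, and nothing in trial conduct changes.

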### **8.2.14. Definition of FAP-Related Events or Serious and Unexpected Toxicity**

The time from the date of randomization to the date of the first occurrence of any FAP-related event at any disease site (colon/rectum/pouch, duodenum) will lead to discontinuation of the study treatment. Follow-up of the subject for FAP-related events will continue, per protocol, until the end of the 30 day post-treatment.

FAP-related primary events by disease site are as follows:

1. Pre-operative, intact colon:
  - a) Disease progression^ indicating need for colectomy with IRA or total proctocolectomy
2. Rectum or pouch events include one or more of the following:
  - a) Excisional intervention by surgical snare or trans-anal excision to remove any polyp  $\geq 10$  mm in size (per pathology report) and/or pathologic evidence of high grade dysplasia.\*
  - b) Disease progression^ indicating need for proctectomy
  - c) Disease progression^ indicating need for pouch resection
  - d) Development of cancer in rectum or pouch
  - e) Death
3. Duodenal disease includes the following:
  - a) Progression in Spigelman Stage to more advanced stage (Stage 2, 3 or 4), refer to Appendix A
  - b) Disease progression indicating need for excisional intervention (sub-mucosal resection, trans-duodenal excision, ampullectomy, duodenectomy, Whipple procedure)
  - c) Development of cancer
  - d) Death

Note, excisional intervention may include open surgery, trans-anal surgery or endoscopic excisions/snare but does not include cautery ablations or hot biopsy.

\*For those subjects stratified to the duodenal group, all concurrent rectal pouch polyps  $> 5$  mm must have been removed at baseline for this event to apply.

^Disease progression is based on endoscopic evaluations compared to baseline demonstrating a clinically significant increase in number and/or size of polyps (~25% increase in disease burden), presence of a large sessile or ulcerated adenoma not amenable to removal, high grade dysplasia in any adenoma, or in-situ or invasive cancer.

Discontinuation from study treatment due to a potential treatment related serious adverse event may include the following:

- Gastrointestinal hemorrhage,  $\geq$  grade 3
- Tinnitus  $\geq$  grade 2, or clinical hearing impairment  $\geq$  grade 3

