For the anticipated range of hazard ratios, 25 to 49 events would be needed for each two-group comparison at the 2-sided 0.05 level to achieve 85% power [3, 4]. Assuming two-year event proportions of 70% in either of the two single-agent groups and 30% to 40% in the combination arm with 50 patients per arm, the expected number of patients with an FAP-related event in either of the two single-agent groups would be 35 and 15 - 20 in the combination arm. The study design expectation is to have 50 - 55 patients with a FAP-related event in each two arm comparison, achieving at least 85% power under the design alternative. The standard deviation around the expectation of 55 events is 4.74, so observing the required number of 49 events or more would be highly likely (the probability is about 91%). If the total number of events in either comparison were only 43, there will still be 80% power to declare a significant treatment

difference under the design alternative of 0.4243.

As the two-year event proportion in the combination arm decreases from 40% with a corresponding decrease in the hazard ratio, the likelihood of observing the required number of events to maintain 85% power actually increases. For example, at the lower expectation of 50 events arising from an assumed two-year event proportion of 30% in the combination arm, the standard deviation of the total number of events in a two-arm comparison decreases to 4.58 and the probability that the observed number of events will exceed the 25 required to achieve 85% at a HR of 0.30 is virtually certain.

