### 7.2 Draft Tables, Listings and Figures

The TLF (Tables, Listings, Figures) templates and shells are noted as Ver. 2.0, October 6, 2014 (SAP Ver. 3.0 September 30, 2014) based on revision provided from Data Management/Statistical Group at Ockham now Chiltern. These draft templates have been removed as an Appendix to the amended SAP and are available upon request.

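### Arms are compared on crude adverse-event incidence although the efficacy event stops drug, so time on drug can differ by arm; supplementary exposure-adjusted rates and a before/after-event count are missing

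*SAP*

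**What the plan says.** SAP 5.5.5 and Protocol 12.6.3 count as treatment-emergent "any adverse event that occurs after administration of the first dose of study drug and through 30 days after the last dose". Baseline conditions that worsen on treatment count too. Tables are given overall, by arm and by cell. Where appropriate, "statistical comparisons between treatment arms will be provided using the above-mentioned methods for analysis of categorical data". Those methods are in SAP 5.5.4: chi-squared techniques on patient counts, where "the Cochran-Mantel-Haenszel one degree of freedom test will be used to reflect the stratified randomization".

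Protocol 8.2.14 states that the first occurrence of "any FAP-related event at any disease site (colon/rectum/pouch, duodenum) will lead to discontinuation of the study treatment". Protocol 11.7 continues adverse-event collection for 30 days after the last dose. Under Protocol 3.2, subjects without an event stay on drug for 24 to 48 months.

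Some FAP events are themselves procedures. Rectum/pouch item 2a in Protocol 8.2.14 is "Excisional intervention by surgical snare or trans-anal excision to remove any polyp" of at least 10 mm and/or with high grade dysplasia. A note adds that "excisional intervention may include open surgery, trans-anal surgery or endoscopic excisions/snare but does not include cautery ablations or hot biopsy".

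The visible text of both documents gives no person-time rate, no time-to-first-adverse-event analysis and no split at the FAP event. It does provide a separate table of treatment-related events and patient-level listings of deaths, serious events and events leading to discontinuation. On the table shells, SAP 7.2 says: "These draft templates have been removed as an Appendix to the amended SAP and are available upon request".

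**The concern.** Crude incidence compares arms fairly when they are at risk for similar lengths of time. Here the efficacy outcome ends treatment, and the plan expects that outcome to be unequal. Per 50 patients, it puts the number with an event "in either of the two single-agent groups would be 35 and 15 - 20 in the combination arm". If that happens, combination patients spend longer on drug and have more time to report any adverse event, even when the drug hazard is the same.

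A second effect runs the other way. Excising a polyp can cause bleeding or perforation (Protocol 3.1), and Appendix E gives perforation, hemorrhage and pancreatitis as complications of duodenal endoscopic treatment. Protocol 5.2.1 lists the same three for NSAIDs including sulindac. When the procedure falls in the 30-day window, its complications count as treatment-emergent, and they fall more often on the arms with more FAP events.

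At stake is how the by-arm safety tables are read, above all for common events. The efficacy conclusion is not affected.

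**Working it through.** **The plan's own figures.** The design hazard ratio is ln(0.60)/ln(0.30) = 0.4243. Events for 85% power at two-sided 0.05 are 4(1.960 + 1.036)²/(ln HR)², which gives 48.9 at 0.4243 and 24.8 at 0.30. These match the stated 49 and 25 in SAP 5.3. The documents state no figure for adverse-event exposure.

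**Inputs.** 171 randomized, so 57 per arm (Protocol 3.2). Stop at 90 FAP events (Protocol 4.2). 53 events by June 2017 (Protocol 3.2). Assumptions: exponential event times, common follow-up T, no other dropout, and a constant adverse-event hazard equal in all arms.

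**Event split.** Let s be the event-free proportion in a single-agent arm. Solve 57·[2(1 − s) + 1 − s^HR] = events.

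**Drug time.** With λT = −ln s for a single-agent arm and HR·λT for the combination, mean time on drug is T(1 − e^(−λT))/(λT). T cancels in the ratio of the arms. At 90 events and HR 0.4243, s = 0.3792, so λT is 0.970 and 0.411. The means are then 0.6208/0.970 = 0.640T and 0.3373/0.411 = 0.820T.

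| Events | HR | Event proportion, single agent vs combination | Drug-time ratio, combination/single agent |
|---|---|---|---|
| 90 | 0.4243 | 62.1% vs 33.7% | 1.28 |
| 90 | 0.7 | 56.8% vs 44.4% | 1.12 |
| 90 | 1 | 52.6% vs 52.6% | 1.00 |
| 53 | 0.4243 | 37.5% vs 18.1% | 1.14 |

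**Effect on crude incidence (90 events, HR 0.4243, no true drug difference).** The incidence of an adverse event with hazard h before drug stops is h/(h + λ)·(1 − e^(−(h+λ)T)). Set h so that the single-agent incidence is B, then apply the same h in the combination arm. The standard error of the difference is √[p₁(1 − p₁)/57 + p₂(1 − p₂)/57].

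| B, single agent | Combination | Difference, points | Standard error, points |
|---|---|---|---|
| 1% | 1.3% | 0.3 | 2.0 |
| 5% | 6.4% | 1.4 | 4.3 |
| 10% | 12.7% | 2.7 | 5.9 |
| 20% | 25.2% | 5.2 | 7.8 |
| 40% | 49.3% | 9.3 | 9.3 |

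At HR 0.7 the last three differences are 1.1, 2.2 and 4.0 points; at HR 1 they are zero.

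**Procedure complications.** Protocol Appendix E gives a 17% complication rate, for duodenal endoscopic treatment only. No rectal rate is given, so 5% is used as a low alternative (assumption). The share of event subjects with a procedure inside the window is taken as 25% to 50% (assumption). The excess in a single-agent arm at 90 events is the 28.35-point gap × rate × share:
- at 17%: 28.35 × 0.17 × 0.25 = 1.2, up to 2.4 points;
- at 5%: 0.4 to 0.7 points.

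Combining both effects for rare events (B from 1% to 5%) gives a net shift, combination minus single agent, of −2.1 to +0.2 points at 17% and −0.4 to +1.0 at 5%. The sign is not determined.

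**The case against.** Crude incidence with related-event tables and patient listings is a defensible plan, and several counter-arguments stand.

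- **Rare serious GI events are already visible.** A reader might infer that the plan cannot separate a post-excision bleed from a drug bleed. The documents do not support that. SAP 5.5.5 lists serious events and discontinuations patient by patient with further relevant information, and for one or two cases a listing is the right tool. Blinded attribution hides the arm, but the investigator still knows that a polyp was just removed.
- **The procedure effect may be smaller than the upper figures.** They apply a duodenal rate to all sites. The clearest case of a procedure in the window is rectal/pouch excision, which has no stated rate. Spigelman progression needs no procedure, and Protocol 8.2.8 expects some surgery after the 30-day contact.
- **The overlap with sulindac differs by comparison.** Both arms of the first comparison contain sulindac. Mistaking procedure harm for a sulindac effect is mainly a risk in CPP-1X versus combination.
- **Both mechanisms need an efficacy difference.** At hazard ratio 1 neither operates.
- **The shells sit outside the SAP**, so an exposure or timing display there cannot be ruled out.

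What remains is unequal drug time in the by-arm incidence comparison. Listings do not adjust for it, and it grows with how common the event is.

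**Conclusion.** The point holds as a modest reporting improvement. If the combination is effective, the stated by-arm comparison is biased toward higher crude incidence in the combination arm even when adverse-event hazards are equal. The bias is under 2 points for rare events and about 3, 5 and 9 points at 10%, 20% and 40% single-agent incidence. It does not exceed one standard error in any case shown. The figures are illustrative: they rest on the design hazard ratio, 90 events, exponential times and common follow-up, and they fall to less than half at hazard ratio 0.7.

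Two stronger readings should be resisted. A reader might carry the design hazards out to 24 to 48 months and get drug-time ratios of 1.35 to 1.66. Those hazards imply about 103 events at 24 months and 140 at 48, beyond the stop at 90. A reader might also conclude that procedure complications materially distort the safety comparison in a known direction. The net shift for rare events runs from about −2 to +1 points on assumed inputs, so neither its size nor its sign can be claimed. The primary analysis is unaffected.

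**What to change.** Keep the full treatment-emergent table and the 30-day window. Add to SAP 5.5.5 and Protocol 12.6.3:

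1. Supplementary by-arm exposure-adjusted rates for serious events, for GI bleeding, perforation and pancreatitis, and for common treatment-emergent events. Use one time-at-risk rule for every subject: first dose to the first such event or, if none, to 30 days after last dose. Risk time should not end at the FAP event for some subjects and 30 days after last dose for others.
2. A descriptive by-arm count of those GI events and serious events by onset: before, versus on or after, the FAP event or excision date. Attach no test and exclude nothing from the main comparison, because post-excision bleeding can be drug-related.

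The cost is two tables and one derived flag from dates already collected. Person-time rates assume a roughly constant hazard, and exposure is itself affected by treatment. The rates also do not remove procedure complications; only the second table shows them. Both should therefore be read beside the crude table.
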